# **ASSESSMENT OF EFFICACY**

# **Primary Efficacy Endpoint:**

Percentage in each group with SUA levels <360µmol/L (the saturation point form sodium urate crystal formation).

# **Secondary Efficacy Endpoints:**

Percentage in each group with reduced number of acute attacks in the second year of the study

Quality of life scores (SF36 and GAQ) at end point compared to baseline in each group and comparison of endpoint QOL scores between the two groups.

Reduction in size and number of tophi.

# Assessment of safety

The nurse intervention reflects recommended best practice involving ULTs that are recommended and licensed for this purpose. Participants will report any adverse events to the nurse. If benzbromarone is prescribed recommended checking of blood liver function tests will be undertaken.

# Procedures for missing, unused and spurious data

If participants leave the study for any reason or if there are omitted data we will use multilevel models for any missing outcome measures and an intention to treat (ITT) analysis.

# **Definition of populations analysed**

All patients randomised into the study will be analysed using an ITT analysis and LOCF for any missing data.

# **ADVERSE EVENTS**

Page 22 of 30 Final version 4 – 6 February 2013

The nurse intervention which is being tested in this study reflects recommended best practice and utilises ULT that is recommended and licensed for this purpose. Therefore, the occurrence of adverse events as a result of participation within this study is not expected and no adverse event data will be collected.

Self- reported adverse events in participants in the nurse intervention will be recorded and if judged to be due to ULT the drug will be stopped and an alternative ULT considered (i.e. as recommended in current guidelines). Known side effects of ULT (e.g. allopurinol, febuxostat, benzbromarone) will be reported to the MHRA using the Yellow Card system, in line with recommended practice, but will not be classed as adverse events with respect to the intervention and will therefore not be reported to the NRES as such. However, a summary of the side effects reported using the Yellow Card system will be included in the final summary submitted to NRES. Adverse events that are unrelated to the nurse intervention and ULT will be treated by the participant's general practitioner, as usual, and again not be reported to the REC.

To ensure clinical governance if the nurse is unsure of causality with respect to ULT she can involve the opinion of [name] (or in his absence [name] or [name]).

Adverse events occurring in the standard care group will be assessed and managed as part of normal care by the general practitioner and will not be reported to the REC.

# **COST EFFECTIVENESS AND UTILITY**

The direct and indirect costs related to gout and its management during the two year study period will be estimated in the nurse led intervention group by recording of the following data:

number of nurse appointments and telephone contacts; duration of each contact; cost of drugs and blood tests; days off work because of acute attacks; any additional health care utilisation during acute attacks. Identical data will be obtained in the standard care group apart from the duration of each GP contact related specifically to gout management – a mean value will be estimated.

Cost utility will be estimated in each group utilising the direct and indirect costs and the SF6D (derived from the SF36). Quality of life during acute attacks will also be obtained in both groups (SF36) and this will be utilised in the cost utility estimations.

# ETHICAL AND REGULATORY ASPECTS

# **Involvement of General Practitioner**

**Nurse led group (RCT):** GPs will be informed if their patients are randomised to the nurse led group and will be kept informed with respect changes to their patients' gout medications. If the nurse detects any adverse event or comorbidity unrelated to gout and its management the GP will also be directly informed.

**Standard care group (RCT):** We will not inform the GP that their patient has been randomised to the ongoing standard care group since this may 'contaminate' the GP care and the GPs in that practice will already have agreed for their patients to be approached for the purposes of this study

Page 23 of 30 Final version 4 – 6 February 2013

# ETHICS COMMITTEE AND REGULATORY APPROVALS

The trial will not be initiated before the protocol, informed consent forms and participant information sheets have received approval / favourable opinion from the Research Ethics Committee (REC), and the respective National Health Service (NHS) Research & Development (R&D) department. Should a protocol amendment be made that requires REC approval, the changes in the protocol will not be instituted until the amendment and revised informed consent forms and participant and GP information sheets (if appropriate) have been reviewed and received approval / favourable opinion from the REC and R&D departments. A protocol amendment intended to eliminate an apparent immediate hazard to participants may be implemented immediately providing that the REC are notified as soon as possible and an approval is requested. Minor protocol amendments only for logistical or administrative changes may be implemented immediately; and the REC will be informed.

The trial will be conducted in accordance with the ethical principles that have their origin in the Declaration of Helsinki, 1996; the principles of Good Clinical Practice, and the Department of Health Research Governance Framework for Health and Social Care, 2005.

# INFORMED CONSENT AND PARTICIPANT INFORMATION

The process for obtaining participant informed consent or assent will be in accordance with the REC guidance, and Good Clinical Practice (GCP) and any other regulatory requirements that might be introduced. The investigator or their nominee and the participant shall both sign and date the Informed Consent Form before the person can participate in the study.

The participant will receive a copy of the signed and dated forms and the original will be retained in the Trial Master File.

The decision regarding participation in the study is entirely voluntary. The investigator or their nominee shall emphasize to them that consent regarding study participation may be withdrawn at any time without penalty or affecting the quality or quantity of their future medical care, or loss of benefits to which the participant is otherwise entitled. No trial-specific interventions will be done before informed consent has been obtained.

The investigator will inform the participant of any relevant information that becomes available during the course of the study, and will discuss with them, whether they wish to continue with the study. If applicable they will be asked to sign revised consent forms.

If the Informed Consent Form is amended during the study, the investigator shall follow all applicable regulatory requirements pertaining to approval of the amended Informed Consent Form by the REC and use of the amended form (including for ongoing participants).

# **RECORDS**

# **Case Report Forms**

Each participant will be assigned a trial identity code number, for use on CRFs other trial documents and the electronic database. The documents and database will also use their

Page 24 of 30 Final version 4 – 6 February 2013

initials (of first and last names separated by a hyphen or a middle name initial when available) and date of birth (dd/mm/yy).

CRFs will be treated as confidential documents and held securely in accordance with regulations. The investigator will make a separate confidential record of the participant's name, date of birth, local hospital number or NHS number, and Participant Trial Number (the Trial Recruitment Log), to permit identification of all participants enrolled in the trial, in accordance with regulatory requirements and for follow-up as required.

CRFs shall be restricted to those personnel approved by the Chief or local Principal Investigator and recorded on the 'Trial Delegation Log.'

All paper forms shall be filled in using black ballpoint pen. Errors shall be lined out but not obliterated by using correction fluid and the correction inserted, initialled and dated.

The Chief or local Principal Investigator shall sign a declaration ensuring accuracy of data recorded in the CRF.

# **Source documents**

Source documents shall be filed at the investigator's site and will include but are not limited to, consent forms, history and examination findings, questionnaires and laboratory results and a record of initiated or altered treatments. Only trial staff as listed on the Delegation Log shall have access to trial documentation other than the regulatory requirements listed below.

#### Direct access to source data / documents

The CRF and all source documents, including progress notes and copies of laboratory and medical test results shall made be available at all times for review by the Chief Investigator, Sponsor's designee and inspection by relevant regulatory authorities.

# **DATA PROTECTION**

All trial staff and investigators will endeavour to protect the rights of the trial's participants to privacy and informed consent, and will adhere to the Data Protection Act, 1998. The CRF will only collect the minimum required information for the purposes of the trial. CRFs will be held securely, in a locked room, or locked cupboard or cabinet. Access to the information will be limited to the trial staff and investigators and relevant regulatory authorities (see above). Computer held data including the trial database will be held securely and password protected. All data will be stored on a secure dedicated web server. Access will be restricted by user identifiers and passwords (encrypted using a one way encryption method).

Electronic data will be backed up every 24 hours to both local and remote media in encrypted format.

# **QUALITY ASSURANCE & AUDIT**

# **INSURANCE AND INDEMNITY**

Insurance and indemnity for trial participants and trial staff is covered within the NHS Indemnity Arrangements for clinical negligence claims in the NHS, issued under cover of

Page 25 of 30 Final version 4 – 6 February 2013

HSG (96)48. There are no special compensation arrangements, but trial participants may have recourse through the NHS complaints procedures.

The University of Nottingham has taken out an insurance policy to provide indemnity in the event of a successful litigious claim for proven non-negligent harm.

# TRIAL CONDUCT

Trial conduct will be subject to systems audit of the Trial Master File for inclusion of essential documents; permissions to conduct the trial; Trial Delegation Log; CVs of trial staff and training received; local document control procedures; consent procedures and recruitment logs; adherence to procedures defined in the protocol (e.g. inclusion / exclusion criteria, correct randomisation, timeliness of visits) and adverse event recording and reporting.

Our Senior Research Nurse will observe each research nurse taking consent in a small sample of study participants to ensure consent is being undertaken in line with GCP guidelines and training provided.

The Trial Co-ordinator and CTU representatives will carry out a site systems audit at least yearly and an audit report shall be made to the Trial Steering Committee.

# TRIAL DATA

Monitoring of trial data shall include confirmation of informed consent; source data verification; data storage and data transfer procedures; local quality control checks and procedures, back-up and disaster recovery of any local databases and validation of data manipulation. The Trial Co-ordinator and CTU representative will carry out monitoring of trial data as an ongoing activity.

Entries on CRFs will be verified by inspection against the source data. A sample of CRFs (10% or as per the study risk assessment) will be checked on a regular basis for verification of all entries made. In addition the subsequent capture of the data on the trial database will be checked. Where corrections are required these will carry a full audit trail and justification.

Trial data and evidence of monitoring and systems audits will be made available for inspection by REC as required.

# RECORD RETENTION AND ARCHIVING

In compliance with the ICH/GCP guidelines, regulations and in accordance with the University of Nottingham Research Code of Conduct, the Chief or local Principal Investigator will maintain all records and documents regarding the conduct of the study. These will be retained for at least 7 years or for longer if required. If the responsible investigator is no longer able to maintain the study records, a second person will be nominated to take over this responsibility.

The Trial Master File and trial documents held by the Chief Investigator on behalf of the Sponsor shall be finally archived at secure archive facilities at the University of Nottingham. This archive shall include all trial databases and associated meta-data encryption codes.

Page 26 of 30 Final version 4 – 6 February 2013

# DISCONTINUATION OF THE TRIAL BY THE SPONSOR

The Sponsor reserves the right to discontinue this trial at any time for failure to meet expected enrolment goals, for safety or any other administrative reasons. The Sponsor shall take advice from the Trial Steering Committee and Data Monitoring Committee as appropriate in making this decision.

# STATEMENT OF CONFIDENTIALITY

Individual participant medical information obtained as a result of this study are considered confidential and disclosure to third parties is prohibited with the exceptions noted above. Participant confidentiality will be further ensured by utilising identification code numbers to correspond to treatment data in the computer files.

Such medical information may be given to the participant's medical team and all appropriate medical personnel responsible for the participant's welfare.

Data generated as a result of this trial will be available for inspection on request by the University of Nottingham representatives, the REC, local R&D Departments and the regulatory authorities.

# PUBLICATION AND DISSEMINATION POLICY

The study results will be submitted to Arthritis Research UK, regulatory authorities, and peer reviewed journals for publication. In addition, the results will be presented at national and international conferences. Study participants' identity will not be disclosed when publishing the results.

Study participants will also be informed of the results, if requested.

# **USER AND PUBLIC INVOLVEMENT**

We have audited the standard of care of gout in the Nottingham Community and subsequently undertaken qualitative research during Phase I of the Nottingham Gout Treatment Trial to ascertain patients' understanding and views on gout and its treatment. The findings from this qualitative research and the results from Phase 1 have been used to develop the nurse intervention package of care which is being delivered in Phase 2 of this study. The nurse led intervention incorporates recommended best practice published by the British Society for Rheumatology and the European League Against Rheumatism.

# STUDY FINANCES

# **Funding source**

This study is funded by Arthritis Research UK.

# Participant stipends and payments

Participants will not be paid to participate in the trial.

Page 27 of 30 Final version 4 – 6 February 2013

# **Appendix 1 – RCT Participant Involvement:**

Page 30 of 30 Final version 4 – 6 February 2013

[Type here] [Type here]

# A community based randomised controlled trial comparing nurse-led intervention with standard care

# -Analysis plan

Synopsis of the design: A 2 year community based randomised controlled trial will be undertaken in Nottingham to investigate clinical effectiveness and cost-effectiveness of a nurse-led quality of care intervention versus standard of care control. A questionnaire survey will be undertaken in the GP practices in Nottinghamshire to obtain 724 patients with gout according to the American College of Rheumatology (ACR) criteria and at least one acute attack in the past year. They will be randomly allocated to the intervention and the control group using stratified (according to the participated GP practices), block (fixed block of 4 for random allocation to keep the balance between the groups) randomisation method. Participants will be examined at baseline, 12 months and 24 months for outcomes such as serum uric acid (SUA), number of acute attacks in the previous year and quality of life (QoL) (SF36).

Principles of analysis: Intention to treat (ITT) analysis will be conducted. Descriptive analysis on raw differences between groups at baseline, 12 months and 24 months will be undertaken. Multi-level regression model (MLM) will be used for the overall comparison of the treatment effect between groups with repeated measures and missing data. We shall include all data from 3 time points in the same model, with repeated measures as level 1 units and individuals as level 2 units. The treatment group and time points will be considered as covariates in the model together with covariates at baseline for the adjustment purpose. Continuous data (eg, SUA, QoL score, etc) will be analysed using MLM linear regression, whereas dichotomous and categorical data will be analysed using MLM logistic or multinomial models. Comparison will be made between the intervention and the control in the RCT, as well as between the control in the RCT and the observational group.

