	individualised lifestyle modification advice and ULT to reduce SUA to below the saturation point for sodium urate crystal formation (360 µmol/L). Individuals in this group will be followed up regularly according to their clinical need/monitoring requirements.  Standard care/control participants will have a single nurse contact at baseline during which they will be provided with the Arthritis Research UK leaflet on gout and be informed on appropriate management of acute attacks. There will be no discussion on other aspects of gout management – if asked about lifestyle and ULT participants will be asked to question their GP about this. This group will be asked to provide a blood sample at 0, 12 and 24 months and also keep a diary of acute attacks over the next 2 years and complete a questionnaire (including QOL assessment) at 12 and 24 months.
Duration of study  Randomisation and blinding	Total – 3 years Per participant – 2 years Planned recruitment start date 1 January 2013 Study participants in the RCT will be aware that they have been randomised to either a nurse-led intervention or to continue standard care/GP-led management.
	Randomisation will be undertaken by the CTU using a web based, computer generated, stratified (by GP practice) random block system and undertaken by the CTU. Following randomisation participants and nurses will obviously both know which group they are in. Although participants will be aware that the study objective is to compare cost effectiveness of nurse versus doctor led management of gout they will not be informed prior to randomisation concerning the recommended best practice strategies which include ULT and treating to target.
Outcome measures	Primary outcome – SUA of <360 µmol/L at study end Secondary outcomes – reduction in number of self-reported acute attacks in year two; improved QOL scores (SF36, Gout Assessment Questionnaire - GAQ); reduction in tophus size and number; cost effectiveness and cost utility based on health utilisation cost and SF6D (derived from SF36).

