### **RANDOMIZATION**

At the initial visit the nurse will answer any further queries concerning the study and obtain written consent to participate. Random allocation will be undertaken using computer generated random numbers. Immediately following written consent, the nurse will phone into Academic Rheumatology, the administrative team will generate the group allocation via the website. Once allocated the patient will be informed of which group they are in. The study number will be used as the patient ID to de-identify the patient information throughout the study.

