### **STATISTICS**

### Methods

The trial statistician ([name]) will oversee the data management, evaluation and analyses. The database will be developed in collaboration with the CTU using access and analysed using SPSS. SUA will be analysed at baseline, 12 months and 24 months. Comparison will be undertaken between the nurse led intervention and control at each observational point. There will be no interim analyses for efficacy or safety. Intention to

Page **19** of **29** Final version 8 –18 May 2015

treat (ITT) analysis will be undertaken to compare treatment effects between groups. Multilevel models will be used for any missing outcome measures. Chi-square test will be used for dichotomous or categorical data and ANOVA test will be used for continuous variables. Adjustment will be made for baseline co-variables as appropriate. Cost per QALY will be estimated from the SF6D and the direct and indirect costs related to gout and its management.

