# 2. Secondary outcomes

- Number of acute attacks in preceding year, year 1 and year 2 within each group and between groups
- Number of patients with tophi at baseline, 12 months and 24 months with each group and between groups
- Mean QoL scores (overall, different domain scores of SF36 and the Gout
   Asssessment Questionnaire (GAQ) including the Gout Impact Scale (GIS) of the GAQ.
   at 0, 12 and 24 months within each group and between groups
- Mean change of QoL scores from baseline to 12 months and 24 months within each group and between groups

**Covariates and baseline predictors:** age, gender, body mass index, disease duration, tophi, associated comorbidity etc.

Task allocation and timetable: The Nottingham CTU will undertake randomisation, development of the database for RCT and the web-based data entry platform. CTU will also conduct data monitoring and quality control for the RCT data. Academic Rheumatology will recruit patients, enter the data through a web-based data entry platform for the RCT data and develop an independent database for the observational group. Both datasets are not open for any interim analysis between baseline and 24 months to keep the randomisation. Analysis will start after 24 months when the data has been fully completed, quality checked over and closed. Analysis for clinical effectiveness (efficacy and side effects) will be completed in 3 months after the closing date of the data. Analysis for cost-effectiveness will be completed in 12 months, as it requires acquisition of additional data for cost. In brief:

- Recruitment 8 months
- RCT and observation 24 months
- Results for clinical effectiveness 3 months
- Results for cost-effectiveness 12 months

Economic Analyses Plan.

Two economic analyses are planned: the first being an economic analysis alongside the RCT and the second modelling the costs and benefits over a longer time horizon. The base case in both models would use an NHS perspective, with a societal perspective (that include indirect costs such as lost productivity) being undertaken in a sensitivity analysis.

Economic analysis alongside the RCT

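### Randomisation is stratified by GP practice but no stated analysis includes practice, a small and conservative fault; the two descriptions of the blocking also need reconciling

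*Supplement*

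**What the plan says.** **Randomisation.** The analysis plan (synopsis of the design) describes allocation as "stratified (according to the participated GP practices), block (fixed block of 4 for random allocation to keep the balance between the groups"). Protocol version 8 (Synopsis, Randomisation and blinding) describes a "web based, computer generated, stratified (by GP practice) random block system" and gives no block size.

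**Analysis.** The plan (Principles of analysis) builds its multilevel model "with repeated measures as level 1 units and individuals as level 2 units"; there is no third level. Its covariates are "age, gender, body mass index, disease duration, tophi, associated comorbidity etc". The protocol (Statistics, Methods) says: "Chi-square test will be used for dichotomous or categorical data and ANOVA test will be used for continuous variables". It allows adjustment for baseline variables but names none.

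**Who sees what.** Under Randomization, the protocol has the nurse take consent: "At the initial visit the nurse will answer any further queries concerning the study and obtain written consent to participate". Allocation comes next: "Immediately following written consent, the nurse will phone into Academic Rheumatology, the administrative team will generate the group allocation via the website". The Synopsis adds: "Following randomisation participants and nurses will obviously both know which group they are in".

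**The concern.** A trial that balances its arms within practices should be analysed with practice in the model. Practice is plausibly prognostic here, because control participants stay under their own GP's care and the protocol's background describes GP management of gout as often suboptimal. If practices differ in outcome, balancing removes that variation from the treatment comparison, but an analysis without practice still counts it as noise. Standard errors then come out too large, and some of the precision bought by stratifying is lost.

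The blocking raises a separate question. A constant block of four within a practice lets anyone who has followed that practice's sequence work out some later allocations. In an open trial this could influence who is approached or confirmed as eligible. The documents describe the blocking in two different ways and do not say who knew the block size.

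**Working it through.** The documents give no figure for either effect, so there is none to reproduce.

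**1. Omitting practice (continuous outcomes)**

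Inputs: 233 evaluable patients per arm (protocol, Power calculations). The practice ICC, meaning the share of outcome variance that lies between practices, is not in the documents; 0.01 to 0.10 is an assumption. As a benchmark effect I use d = 0.26, the standardised difference at which 233 per arm gives 80% power.

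With arms balanced within practices, the true variance of the difference is (1 − ICC) times the variance an unstratified analysis assumes. Hence:

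- SE overstatement = 1/√(1 − ICC) − 1
- actual two-sided alpha = 2Φ(−1.96/√(1 − ICC))
- with SE₀ = √(2/233) = 0.0927 and SE₁ = SE₀√(1 − ICC), power without practice = Φ((d − 1.96·SE₀)/SE₁) and power with practice = Φ(d/SE₁ − 1.96)

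| Assumed ICC | SE too large by | Actual alpha | Power without practice | Power with practice |
|---|---|---|---|---|
| 0.01 | 0.5% | 0.049 | 80.3% | 80.5% |
| 0.02 | 1.0% | 0.048 | 80.4% | 80.9% |
| 0.05 | 2.6% | 0.044 | 80.7% | 82.1% |
| 0.10 | 5.4% | 0.039 | 81.4% | 84.1% |

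The formula assumes complete balance in every practice. Unfinished blocks give less, so at a given ICC these are upper figures.

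**2. Predictability, if blocks were always four**

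There are six equally likely orderings of two A and two B. The fourth allocation is always determined by the first three. The third is determined when the first two match, with probability 1/3. So 1 + 1/3 = 1.33 of every 4 allocations (33.3%) are certain in a complete block. Always guessing the arm with more places left is right 2.83 times in 4 (70.8%), against 50% by chance.

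The number of participating practices is not given, so a range is needed:

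| Patients per practice | Certain | Calculation |
|---|---|---|
| 3 | 11.1% | (1/3)/3 |
| 4 or 8 | 33.3% | complete blocks |
| 5 | 26.7% | 1.33/5 |
| 10 | 26.7% | 2.67/10 |
| 17 | 31.4% | 5.33/17 |

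Three per practice corresponds to all 170 Nottinghamshire practices taking part (512/170 = 3.01); the best guess is then right 61% of the time. With one or two patients in a practice, none is certain. All these figures require full knowledge of the sequence within the practice.

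**3. Are any allocations still to be made?**

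The list of changes at the front of the supplement puts study end at 31 December 2016. The protocol ends the trial at the last participant's last visit and gives each participant two years. Randomisation should therefore have finished by about the end of 2014, before version 8 (18 May 2015).

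**The case against.** **On omitting practice.** The error is in the safe direction and small. The protocol's own figures require 70 per arm for the primary outcome against 256 planned, so the main conclusion is hardly exposed. The plan's covariate list is open-ended and the protocol's adjustment clause is loose, so practice could be let in. For change-from-baseline outcomes, practice effects that stay constant over time cancel. The first two of these points and the last stand, and they limit the weight of the concern. The open wording does not answer it: a design variable would be left to later choice, and the two-level structure as written excludes it.

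A reader might infer that 5% to 10% of the patients are in effect thrown away. That describes interval width. In power terms, at ICC 0.05 and 0.10 the equivalent loss is about 3.5% and 7% (about 18 and 36 of 512), because stratification has already reduced the estimate's true variance.

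**On predictability.** A reader might infer that nurses could foresee allocations and select patients. The documents do not support that:

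- They do not say that nurses worked practice by practice, followed a practice's sequence or knew the block size. They refer to more than one nurse and allow home visits and recruitment by advertisement.
- Allocation is released only after written consent, through a website. For surgery recruits, eligibility is confirmed by telephone before the nurse's visit.
- The later document's wording on blocks is ambiguous and could mean varying sizes.

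What remains is that the two descriptions differ, and that neither document says the block size varied or was withheld from recruiting staff.

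**Conclusion.** The concern holds in a limited form. Practice is the randomisation stratum in both current documents and appears in no stated analysis. For continuous outcomes this overstates standard errors by about 0.5% to 5%, puts actual alpha at about 0.049 to 0.039, and costs at most about 3 points of power near 80%. These figures rest on an assumed ICC of 0.01 to 0.10 and near-complete balance within practices. No false positives arise.

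The formula does not carry over to the logistic model for the primary outcome. Adding a practice intercept there also changes the odds ratio being estimated, so the size of that effect is left open.

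The blocking is a secondary point of reporting. If blocks were always four and the sequence within a practice was known, 11% to 33% of allocations could have been certain at three or more patients per practice. The documents establish the first condition only in the plan and do not establish the second.

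**What to change.** 1. In the analysis plan, add practice as a random intercept (level 3) in every multilevel model, coded as the stratum used at randomisation, including for participants recruited by advertisement. Base the between-arm tests on these models instead of unstratified chi-square and ANOVA. Practices with patients in only one arm need not be pooled when the intercept is random.
2. Reconcile the plan's and the protocol's descriptions of the blocks. Report the block size actually used and who knew it, so that readers can judge concealment.
3. Change the block size only if allocations remain to be made; on the stated timetable none should.

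The cost is one term per model, and it can still be added because the plan starts analysis only after the data are closed. The one drawback is that a three-level logistic model may be hard to fit if practices contribute few patients. The plan should therefore state beforehand what will be reported if it does not converge.
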